Even though SLN mapping with indocyanine green (ICG) shows a consistently high overall detection rate (78-100%) and a high bilateral detection rate (57-97%) in women with cervical cancer < 2 cm and low-risk endometrial cancer (3,18,25-28), the use of SLN mapping in larger cervical and endometrial cancer with high-risk histology is more doubtful. The present study will investigate if the combination of SLN mapping and a preoperative diagnostic FDG-PET/CT improves the detection of metastases in women with large cervical tumours (> 2 cm) and in women with high risk histology endometrial cancer.

Aims of the study

- I. To evaluate the diagnostic safety of SLN mapping in combination with FDG-PET/CT imaging in women with cervical cancer with tumour size > 2 cm and in women with high-risk histology endometrial cancer
- II. To evaluate the course of lymphedema in women with early-stage cervical (tumour > 2 cm) following SLN mapping and PLD.
- III. To evaluate the course of lymphedema following SLN mapping, PLD and PALD in women with high-risk endometrial cancer.

It is hypothesized that SLN mapping in combination with FDG-PET/CT imaging is a diagnostically safe technique in women with high risk cervical cancer (tumour > 2 cm) and in women with high-risk endometrial

It is further hypothesized that PLD- for cervical cancer and PLD+ PALD for high-risk endometrial cancer in combination with SLN mapping will lead to an incidence of chronic lymphedema (as measured 12 months postoperatively) of around 30%, leading to a significantly impaired quality of life.

Study population

- Study IIA: Women with cervical cancer (FIGO stage IB1, IB2 and IIA1) and a tumour size > 2 cm with planned robotic assisted laparoscopic radical surgery including radical hysterectomy and PLD are eligible.
- Study IIB: Women with presumed stage I high-risk endometrial cancer (Endometrioid adenocarcinoma grade 3 or Type 2 histology; serous adenocarcinoma, clearcell adenocarcinoma and carcinosarcoma) (32-33) planned for robotic assisted laparoscopic radical surgery including

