Appendix II. English version of all included PROMs

EORTC IL76

ENGLISH

EORTC IL76

Patients sometimes report that they have the following symptoms or problems. Please indicate the extent to which you have experienced these symptoms or problems during the past week. Please answer by circling the number that best applies to you.

During the past week:

	Not at all	A little	Quite a bit	Very much
55. Have you had swelling in one or both legs?	1	2	3	4
56. Have you felt heaviness in one or both legs?	1	2	3	4
57. Has the skin felt tight in your leg(s)?	1	2	3	4
58. Have you had pain in your leg(s)?	1	2	3	4
59. Have you had swelling in the genital area?	1	2	3	4
60. Has the skin felt tight in your genital area?	1	2	3	4
61. Have you had swelling in your groin?	1	2	3	4
62. Have you had sore skin in your groin?	1	2	3	4
63. Have you had pain in your groin?	1	2	3	4

© Copyright 2020 EORTC Quality of Life Group. All rights reserved.

LYMQOL LEG- Scoring System
Lymphoedema Quality of Life Tool

The score for the individual responses are given below. If the item is not scored and left blank or not applicable this is scored with a 0. Domain totals are calculated by adding the individual scores and dividing the total by the number of questions answered. (If >50% of questions per domain are not answered this cannot be calculated and =0).
 The four domains and their corresponding questions are: Function 1 (a-f), 2,3
 Appearance 4,5,6,7,8,9,10 Symptoms 11,12,13,14,15 and Emotion 16,17,18,19,20,21.
 Overall quality of life (Q22) is scored as the value marked by the patient, between 0-10.

(Q1) How much does your swollen leg affect the following activities?

If any of the items are not applicable to you, please write N/A in the relevant answer box(es)

- a) your walking
- b) your ability to bend, e.g. to tie shoelaces or cut toenails
- c) your ability to stand.
- d) your ability to get up from a chair.
- e) your occupation
- f) your ability to do housework

Not at all	A little	Quite a bit	A lot
1	2	3	4
1	2	3	4
1	2	3	4
1	2	3	4
1	2	3	4
1	2	3	4

(Q2) Does the swelling affect your leisure activities/ social life?

1	2	3	4
---	---	---	---

Please give examples of this

.....

(Q3) How much do you have to depend on other people?

1	2	3	4
---	---	---	---

(Q4) How much do you feel the swelling affects your appearance?

(Q5) How much difficulty do you have finding clothes to fit?

(Q6) How much difficulty do you have finding clothes you would like to wear?

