(Q7) Do you have difficulty finding shoes to fit?

(Q8) Do you have difficulty finding socks/ tights/ stockings to fit?

(Q9) Does the swelling affect how you feel about yourself?

(Q10) Does it affect your relationships with other people?

Not at all	A little	Quite a bit	A lot
1	2	3	4
1	2	3	4
1	2	3	4
1	2	3	4
1	2	3	4
1	2	3	4

Not at all	A little	Quite a bit	A lot
1	2	3	4
1	2	3	4
1	2	3	4
1	2	3	4
1	2	3	4

(Q11) Does your lymphoedema cause you pain?

(Q12) Do you have any numbness in your swollen leg(s)?

(Q13) Do you have any feelings of "pins & needles" or tingling in your swollen leg(s)

(Q14) Does (do) your swollen leg(s) feel weak?

(Q15) Does (do) your swollen leg(s) feel heavy?

In the past week....

(Q16) Have you had trouble sleeping?

(Q17) Have you had difficulty concentrating on things, e.g. reading?

(Q18) Have you felt tense?

(Q19) Have you felt worried?

(Q20) Have you felt irritable?

(Q21) Have you felt depressed?

(Q22) Overall, how would you rate your quality of life at present?
Please mark your score on the following scale:

Please mark your score on the following scale:

0 1 2 3 4 5 6 7 8 9 10
poor excellent

Thank you for completing this form.

If you have any comments or queries about it, please discuss these with

Dr [name], Consultant

Questions 16 to 21 have been reproduced with permission from the EORTC. These questions are only a part of the QLQ-C30 Questionnaire.

Copyright November 2007 Ref LEG VII

All rights reserved. This document can be used or reproduced freely. If all or part of the documents be reproduced, we request that the source and copyright owners be acknowledged. Application for the copyright owners permission should be forwarded in writing to [name], Consultant in Palliative Medicine, Nightingale Macmillan Unit, [name].

EORTC QLQ-C30 (version 3)

We are interested in some things about you and your health. Please answer all of the questions yourself by circling the number that best applies to you. There are no "right" or "wrong" answers. The information that you provide will remain strictly confidential.

Please fill in your initials:

Your birthdate (Day, Month, Year):

Today's date (Day, Month, Year):

31

1. Do you have any trouble doing strenuous activities, like carrying a heavy shopping bag or a suitcase?
2. Do you have any trouble taking a long walk?
3. Do you have any trouble taking a short walk outside of the house?
4. Do you need to stay in bed or a chair during the day?

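### The LYMQOL scoring sheet codes unanswered material as 0 without exempting Q22, where 0 is the worst valid answer, and sets incalculable domains to 0, which is better than the best attainable score

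*Protocol*

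**What the plan says.** Appendix II of the protocol reproduces the LYMQOL LEG questionnaire with its scoring instructions. Four statements matter.

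- Unanswered items: "If the item is not scored and left blank or not applicable this is scored with a 0". No item is excepted.
- Domain scores (Q1 to Q21): "Domain totals are calculated by adding the individual scores and dividing the total by the number of questions answered".
- Domains that are mostly unanswered: "If >50% of questions per domain are not answered this cannot be calculated and =0".
- Overall quality of life: "Overall quality of life (Q22) is scored as the value marked by the patient, between 0-10".

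Q1 to Q21 are coded 1 to 4, with 1 for no problem and 4 for the most. Q22 is printed as "0 1 2 3 4 5 6 7 8 9 10" with the anchors "poor excellent", so 0 is a permitted answer and the worst one.

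The section on patient reported outcome measures gives LYMQOL only to women who report a symptom on the IL76 screening questions. The questionnaires are completed on paper or electronically at 3, 12, 24 and 36 months. Lymphedema and quality of life are secondary outcomes in both studies.

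**The concern.** A code for a missing answer should lie outside the range of real answers. For Q1 to Q21, 0 does. For Q22 it does not: the sheet's only instruction for an unanswered item gives the value that a woman with the poorest quality of life would mark. If data entry follows the sheet, the two cases merge and can be separated only by going back to the form.

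The domain rule has a related weakness in the other direction. A score that the sheet itself says cannot be calculated is nevertheless given a number, and that number lies beyond the favourable end of the scale.

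At stake is the description of quality of life among women with lymphedema symptoms. In its aims, the protocol expects chronic lymphedema in around 30%, "leading to a significantly impaired quality of life". Blank Q22 answers scored 0 would push the Q22 mean towards that expectation. Incalculable domains scored 0 would push the domain means away from it.

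**Working it through.** The protocol states no figure to reproduce. The check sets the scoring rules against the item ranges and then works out the effect on a mean.

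**1. Single blanks in Q1 to Q21.** Valid codes are 1 to 4. Take the Symptoms domain (five items) with answers 2, 2 and 3 and two blanks. The sum with the blanks as 0 is 7. Divided by the three questions answered, it is 7/3 = 2.33, the same as the mean of the answered items. Here the 0 is a harmless filler, provided that a blank is not counted as answered.

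**2. Domains with more than half unanswered.** The lowest score obtainable from answered items is 1 (no problem on every item). The sheet's 0 is below that. It can be recognised as a code, but if it is averaged it counts as better than no impairment. For example, two women scoring 2.33 and one incalculable domain give 2.33 if the third is missing, and (2.33 + 2.33 + 0)/3 = 1.56 if it is averaged as 0.

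**3. Blank Q22.** The valid range is 0 to 10. Zero lies inside it, at the worst end, and Q22 is neither summed nor divided by a count of answers, so nothing removes the filler. Two women marking 7 and one blank give a mean of 7.0 if the blank is missing, and (7 + 7 + 0)/3 = 4.67 under the literal rule.

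**4. Size for Q22.** Let m be the share of LYMQOL respondents who leave Q22 blank, and mu and s the mean and SD among those who answer. With blanks scored 0:

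- mean = (1 - m) x mu, so bias = -m x mu
- variance = (1 - m) x s² + m x (1 - m) x mu²

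The protocol gives none of m, mu or s. All values below are assumptions, and the bias formula takes skipping to be unrelated to the score. With mu = 7 and s = 2:

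| Share blank | Mean | Bias | SD |
|---|---|---|---|
| 2% | 6.86 | -0.14 | 2.21 |
| 5% | 6.65 | -0.35 | 2.48 |
| 10% | 6.30 | -0.70 | 2.83 |
| 20% | 5.60 | -1.40 | 3.32 |

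Over mu from 5 to 8 and m from 2% to 20%, the bias runs from -0.02 x 5 = -0.10 to -0.20 x 8 = -1.60 points on the 0-10 scale. With no blanks it is zero.

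**The case against.** The strongest reply is that Q22 has its own sentence, which scores it as the value the patient marked. An unmarked Q22 then has no score. The layout lends some support: the blank rule is followed at once by the domain calculation, Q22 comes after the list of domains, and the only invitation to write not applicable stands under Q1. This reading is tenable. It does not remove the problem, because the Q22 sentence is silent on an unmarked answer, and the only sentence about unmarked items says 0.

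A second reply is that this is a third-party form reproduced in an appendix, and that the handling of missing items belongs in a statistical analysis plan, which is not at hand. It is right that the absence of a missing-data rule would be no finding. The point here is that the protocol includes a stated rule which gives a wrong value when followed. An analysis plan may override it, but blanks already keyed as 0 from paper would still have to be traced.

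A third reply concerns weight, and it stands. Q22 is one item of a secondary outcome. Only women who screen positive on IL76 complete it, so it has no symptom-free comparison group within LYMQOL. The QLQ-C30 separately asks about overall health and overall quality of life (items 29 and 30). Neither primary outcome is touched.

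A reader might infer that skipped answers will in fact enter as the worst quality of life, or that they will create a false decline from 3 to 36 months. The protocol supports neither. The first depends on which reading data entry adopts. The second needs skipping to rise over time, and nothing in the text indicates that.

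**Conclusion.** The point holds as a defect in a stated scoring rule, of limited weight. Taken literally, the sheet scores a skipped Q22 as the worst valid answer, and the Q22 sentence leaves that case open and does not correct it. The sheet also assigns an incalculable domain a value better than the best attainable score. The two errors run in opposite directions: Q22 towards impairment, the domains towards none.

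The size cannot be determined from the protocol. The figure of -0.35 points rests on an assumed 5% blank and an assumed mean of 7, and illustrates the formula. It is not evidence of material bias in this trial. It would be wrong to conclude that the hypothesised impairment of quality of life would be an artefact of scoring: the QLQ-C30 measures overall quality of life independently of this sheet, and the domain rule biases against the hypothesis.

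**What to change.** Add to the protocol's section on patient reported outcome measures a statement to this effect: *A LYMQOL Q22 that is blank or not applicable is set to missing; the value 0 is recorded only when the patient marked 0. A LYMQOL domain with more than 50% of its questions unanswered is set to missing and not to 0. The blank = 0 code serves only as a filler inside the Q1-Q21 domain sums.*

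Give missing Q22 answers and incalculable domains a separate database code, and check paper forms already entered as Q22 = 0 against the originals.

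The cost is a short scoring statement, a missing-value code and a limited re-check of forms. The downside is a slightly smaller analysed n for these scores, so the number with a valid score should be reported at each visit.

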Removed SLNs are fixed in formalin after excision. A national ultra-staging protocol is implemented in all three participating centres. At the Department of Clinical Pathology the SLNs will be serially sectioned at 2-mm intervals in cross-section and entirely embedded in paraffin. The SLNs will be examined by the ultra-staging protocol consisting of four consecutive sections 5 μ m thick, each obtained at 350 μ m intervals according to the Danish guideline for SLN analysis in breast cancer. The first section at each level is stained with routine hematoxylin and eosin staining, the second section will be used for immunohistochemical staining for cytokeratin AE1/AE3 and the third section is available for additional analysis. Non SLNs will be examined conventionally through microscopy and routine hematoxylin and eosin staining of each block.

Histopathological features that will be recorded include tumor size, presence or absence of lymphovascular space invasion, the number of SLNs per case, the number of nonSLNs per case, the presence of metastases in SLNs and non-SLNs and the size and location of the metastasis in the SLNs.

Patients with histologically verified metastatic disease (including micro metastases) will be allocated to postoperative therapy according to national guidelines. Postoperative clinical follow up will be performed according to national guidelines.

Patient reported outcome measures

A combination of validated questionnaires are completed to assess the incidence of lymphedema and its impact on quality of life:

- Ten questions on lymphedema selected from the European Organization for Research and Treatment of Cancer (EORTC) Vulva Cancer Questionnaire Module (VU34) and included in the EORTC item bank: IL76. The questions will be used to screen for lymphedema, if the patient answers yes to any of the questions, they will be asked to complete the LYMPQOL questionnaire (please see below). Two items in the IL76 constitute a validated scale of leg lymphedema in women with cervical and endometrial cancer as entailed in the questionnaires EORTC CX24 and EN24.
- Lymphedema Quality of Life Questionnaire (LYMQOL) (29). A validated condition-specific quality of life assessment tool (Lymphedema Clinic, Derby Hospital NHS Foundation Trust, England).
- The generic questionnaire, EORTC Quality of Life Questionnaire Core 30 (EORTC QLQ-C30) (30) and the disease specific instruments for cervical (CX-24) and endometrial (EN-24) cancer

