The LYMQOL questionnaire will be translated to Danish using independent forward-backward translation and pilot tested before administration.

The questionnaires are completed as paper/pen version or electronically at the patient's individual preference at 3, 12, 24, and 36 months after surgery. The incidence of early lymphedema will be evaluated at 3 months postoperatively as a difference score between 3 months and the baseline score. The course of chronic lymphedema will be evaluated over time. Written reminders will be sent once after three weeks at each questionnaire interval if the patient has not responded.

Sociodemographic variables will be collected using a questionnaire designed for the purpose and included in the first questionnaire package. The sociodemographic variables include Danish social security number, age, hospital, date of inclusion, BMI, smoking status and contact information. Other data recorded from patient medical files include comorbidity, prior abdominal surgery, type of cancer, presumed preoperative FIGO stage, final FIGO stage postoperatively and whether or not the patient undergoes postoperative oncological therapy. This information will be used for stratification and adjustment in the analyses of lymphedema and quality of life.

Special considerations

In Study IIA radiologically and/or clinically suspected lymph nodes may be sent for frozen section to rule out the metastatic disease. Alternatively, a two-step procedure: removal of suspected lymph nodes for histology as a first step operation followed by completion surgery as a second step, if no metastatic disease in the removed lymph nodes is revealed. If metastatic lymph node involvement is histologically confirmed intra-operatively, the surgical procedure of women with cervical cancer will be terminated and the patient will be referred for chemo-radiotherapy.

In study IIB In case of clinically highly suspicious lymph nodes a frozen section evaluation is recommended, and if metastatic disease is identified, systematic PLD and PALD should be abandoned and replaced by removal of all clinically and by imaging suspicious lymph nodes in the pelvic and paraaortic area. All women with serous adenocarcinomas and with carcinosarcomas should further undergo infracolic omentectomy (31).

Primary outcome measurements

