Study IIA: The overall sensitivity of SLN mapping combined with removal of FDG-PET/CT positive lymph nodes in the detection of lymph node metastases. Due to the low prevalence of the disease this study is primarily explorative.

Study IIB: The NPV of SLN mapping combined with FDG-PET/CT. Please see below for a power calculation.

Secondary outcome measurements

Study IIA:

- Prevalence of lymph node metastasis.
- The detection rate of SLNs. The positive- and negative predictive values of SLN mapping per patient and per hemi-pelvis.
- The positive- and negative predictive value, sensitivity and specificity analyses of FDG-PET/CT.
- The specific size of the cervical tumour determined by a combination of MR imaging, pathology and clinical evaluation will be described for comparison.
- Incidence and severity of lymphedema and quality of life assessment of all patients.

Study IIB:

- Prevalence of lymph node metastasis.
- The detection rate of SLNs in high risk endometrial cancer.
- The sensitivity of SLN mapping per patient.
- Incidence and severity of lymphedema and affection of quality of life after SLN mapping, PLD and PALD.
- Intra- and postoperative complications after surgery with SLN mapping, PLD and PALD.

Statistical analysis

Study IIA cervix cancer:

The exact prevalence of lymph node metastases in cervical cancers of > 2cm is not known from the literature. In studies including low risk cervical cancer patients (tumors < 20 mm) it has been estimated to be < 10%. The present study is explorative and will include 100 patients in Study IIA (cervical cancer) who have undergone PLD after SLN mapping.

Further, the rate of true positive (TP), false positive (FP), false negative (FN) and true negative (TN) findings of PET/CT and SN mapping will be identified to assess the positive predictive value,

the negative predictive value, the sensitivity of PET/CT and SN mapping, respectively. Explorative comparisons will be made for each of the intervention tests (PET/CT and SN mapping).

Study IIB endometrial cancer:

Amendment 04.12.2020

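### The LYMQOL LEG scoring sheet gives a mostly unanswered domain the value 0, below the best attainable score of 1.0, and the protocol never sets it to missing

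*Protocol*

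**What the plan says.** Appendix II of the protocol reproduces the LYMQOL LEG questionnaire together with its scoring sheet. Three rules on that sheet matter here.

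- Single items: "If the item is not scored and left blank or not applicable this is scored with a 0".
- Domains: "Domain totals are calculated by adding the individual scores and dividing the total by the number of questions answered".
- Incomplete domains: "If >50% of questions per domain are not answered this cannot be calculated and =0".

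Response options run from 1 (not at all) to 4 (a lot), so a low score means little impairment. The sheet allocates the items to domains, beginning "The four domains and their corresponding questions are: Function 1 (a-f), 2,3". That makes 8 Function items, followed by 7 for Appearance, 5 for Symptoms and 6 for Emotion. Question 22, overall quality of life, is scored separately from 0 to 10, with 0 at the poor end.

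The section on patient reported outcome measures gives LYMQOL to women who screen positive on the EORTC lymphedema items: "if the patient answers yes to any of the questions, they will be asked to complete the LYMPQOL questionnaire". Questionnaires are scheduled at 3, 12, 24 and 36 months, and "The course of chronic lymphedema will be evaluated over time". The secondary outcomes for Study IIA include "Incidence and severity of lymphedema and quality of life assessment of all patients"; Study IIB has a similar entry. The only text in the body on questionnaire non-response is a single written reminder. No section says what the analysis does with a domain coded 0.

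**The concern.** A score that cannot be calculated should be missing. Here it receives a number, and that number is better than the best score a woman can obtain by answering. At item level the 0 does no harm, because the divisor counts only answered items. At domain level nothing neutralises it.

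If the sheet is followed literally, a woman who leaves most of a domain unanswered counts as at least one point better than a woman who reports no effect at all. Domain means move towards less impairment, which works against the protocol's own hypothesis that chronic lymphedema impairs quality of life. If the share of such domains changes between visits, the apparent course of impairment changes with it: towards improvement when the share rises, towards worsening when it falls.

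The design offers a route to such domains. The screening items printed in Appendix II include genital and groin symptoms, whereas the form that follows concerns the leg, for example "How much does your swollen leg affect the following activities". A woman screened in for groin symptoms alone may find many items irrelevant. Question 1 expressly allows a not-applicable answer, and five such answers among its six parts are enough to set the Function domain to 0.

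**Working it through.** **Inputs from Appendix II of the protocol.** Item codes 1 to 4; domain sizes 8, 7, 5 and 6; domain score = sum of item scores / number of answered items; domain = 0 if more than 50% of its items are unanswered.

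**Inputs that are assumptions.** The share f of non-calculable domains among women completing LYMQOL (5%, 10% and 20% shown) and the mean mu among women with a calculable score (any value from 1.0 to 4.0). The protocol gives neither.

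**Step 1: when the rule applies.** Smallest number of unanswered items above 50%:

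| Domain | Items | Unanswered items that trigger 0 | Fewest answers for a score |
|---|---|---|---|
| Function | 8 | 5 (5/8 = 62.5%) | 4 |
| Appearance | 7 | 4 (4/7 = 57.1%) | 4 |
| Symptoms | 5 | 3 (3/5 = 60%) | 3 |
| Emotion | 6 | 4 (4/6 = 66.7%) | 3 |

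**Step 2: attainable range.** With a answered items, the lowest score is (a × 1)/a = 1.0 and the highest is (a × 4)/a = 4.0, in all four domains. A 0 cannot arise from answers. This holds even if the divisor were taken as all items in the domain: the lowest calculable scores would then be 4/8 = 0.5, 4/7 = 0.57, 3/5 = 0.6 and 3/6 = 0.5, all still above 0.

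**Step 3: effect on a mean.** With zeros kept as numbers, the mean is (1 − f) × mu + f × 0 = (1 − f) × mu. The downward shift is mu − (1 − f) × mu = f × mu. Since mu lies between 1.0 and 4.0, the shift lies between f and 4f.

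| Assumed f | Shift, mu = 1.0 | Shift, mu = 2.0 | Shift, mu = 4.0 |
|---|---|---|---|
| 5% | 0.05 | 0.10 | 0.20 |
| 10% | 0.10 | 0.20 | 0.40 |
| 20% | 0.20 | 0.40 | 0.80 |

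The last column is an outer bound, because it needs every scored woman to mark the worst option on every item. For means of 1.5 to 3.0 the shift at f = 10% is 0.15 to 0.30.

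**Step 4: effect on a change over time.** Hold mu constant and let f rise from 5% to 15% (assumed). The apparent change is −(0.15 − 0.05) × mu, which is −0.10 to −0.40. With mu = 2.0, the mean goes from 0.95 × 2.0 = 1.90 to 0.85 × 2.0 = 1.70, a change of −0.20 with no true change. If f falls by the same amount, the sign reverses.

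**Step 5: one woman, Symptoms domain (constructed example).** At one visit all five items are marked 3: 15/5 = 3.0. At the next, two items are marked 3 and three are blank: 3/5 = 60% unanswered, so the sheet gives 0. The recorded change is −3.0. Her two answered items average 6/2 = 3.0, so her answers did not change. The largest change she could reach by answering is 1.0 − 3.0 = −2.0.

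**Step 6: with such domains set to missing.** Every analysed score lies in 1.0–4.0. A mean of 2.0 among calculable scores stays 2.0, instead of 1.9, 1.8 or 1.6 at f = 5%, 10% or 20%.

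**The case against.** The best reply is that the sentence answers itself. It calls the domain not calculable, so the 0 reads naturally as a no-score code, and because it is out of range it is easy to recognise in a data set. The item rule uses 0 in the same empty sense. On this view, recoding the 0 to missing is routine work for the SAP, which is not shown. The text also belongs to a reproduced third-party form, and the protocol's statistical section gives no rule for analysing any questionnaire. Further, all values of f are assumed, not-applicable answers are invited only under question 1, and the sentence on the course of lymphedema does not name the LYMQOL domains.

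Much of this stands as a limit on weight. The no-score reading is plausible, nothing proves that zeros will be averaged, and the SAP may recode them. The tie to a particular change score is inferred.

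It does not remove the point. The protocol is not silent: it prints a numeric value for a score that it says does not exist. Nor can 0 be treated as missing across the whole form, because on question 22 it is a genuine answer. The distinction has to be stated, and the protocol does not state it.

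**Conclusion.** The concern holds and is minor. The printed rule puts a value outside the attainable 1.0–4.0 range, on the favourable side, in place of a missing domain score, and no part of the protocol excludes it from analysis. Followed literally, it biases a domain mean downward by f × mu, that is by f to 4f points; at an assumed 10% this is 0.10–0.40.

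The size rests on two assumptions: that the zeros enter the analysis as numbers, and the value of f, which the protocol does not give. These figures show sensitivity to the rule and are not a forecast of bias. The scope is the four LYMQOL domain scores among screen-positive women, a secondary patient-reported outcome. The primary sensitivity and NPV outcomes, the EORTC scales and question 22 are unaffected.

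**What to change.** Add one sentence to the section on patient reported outcome measures, or as a note to the scoring sheet: for analysis, a LYMQOL domain with more than 50% of its items unanswered (blank or not applicable) is set to missing and is never entered as 0. It helps to add that this concerns the four domain scores only and that a 0 on question 22 remains a valid answer.

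The cost is that sentence. The questionnaire does not change and no new data are needed.
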